1. PURPOSE OF THE STUDY

a. Brief Summary

The purpose of the study is to determine if there are differences in the final height or hormone profile of patients placed on different forms of aromatase inhibitor now routinely used to increase stature; namely, Anastrozole and Letrozole. It also should determine if there are differences in the side effect profiles of the two drugs to be used. **Objectives**

We hope to learn if there are differences in effects of different forms of aromatase inhibitors on growth. There have been 3 randomized controlled trials using aromatase inhibitors to improve stature in a variety of circumstances (delayed puberty, idiopathic short stature, growth hormone deficiency), but no actual comparative trials between the different forms. We hope to elucidate if there are differences in the growth rates/final heights between the different forms of therapy. This will certainly add to the current, somewhat small literature about the use of these drugs, although they are widely used. We also will look at the differences between the side effect profiles of the two medications. **Rationale for Research in Humans**

Since we are looking at final adult heights, human subjects are necessary.

2. STUDY PROCEDURES

a. Procedures

Patients from our endocrinology practice meeting our inclusion criteria will be consented into the study. They will be randomized into 1 of 2 treatment arms (Anastrozole 1 mg qday or Letrozole 2.5mg qday). Labs (gonadotropins, androgens, estrogens, growth factors, lipid profile) will be done every 6 months, bone age annually, and DEXA scans every 2 years.

We will see the patients annually until near final height (< 2 cm growth velocity per year), re-consenting in those over 18 years old. We will perform physical exams, obtain

anthropometric data, and repeat the above blood tests at least once off medication and perform imaging studies as warranted.

Beginning with this March 2016 renewal, we will no longer randomize to A vs L but use only A, continuing to collect observational data. **Procedure Risks**

We will be using the standard doses for the two drugs used. We will be monitoring with every 6 month physical exams and laboratory evaluation for possible side effects. At the discretion of the investigator, the medication may be reduced or discontinued, specifically if growth velocity falls below normal. **Use of Deception in the Study**

No deception will be used. Use of Audio and Video Recordings

No audio or video recording will occur. Alternative Procedures or Courses of Treatment

There are no alternatives to the above treatment. The only alternative would be to not start on the medication. Growth hormone is a theoretical option but is not standard of care for patients meeting these inclusion criteria. No standard treatment will be withheld. Will it be possible to continue the more (most) appropriate therapy for the participant(s) after the conclusion of the study?

Yes

g. Study Endpoint(s)

Our end point is final height which is defined as less than 2 cm of growth per year. We anticipate that all patients will reach this end point. **BACKGROUND**

a. Past Experimental and/or Clinical Findings

Without estrogen action, the fusion of the growth plates is postponed and longitudinal growth continues. This is the basic idea behind using aromatase inhibitors to augment growth. Aromatase inhibitors block the conversion of testosterone to estrogen leading to more time for skeletal growth. Although aromatase inhibitors have been used widely as a treatment for estrogen responsive breast cancers and in fact there is a plethora of data in that population, to date there have been 3 published randomized control trials using third generation aromatase inhibitors, and only one has been published to final height. The study to final height showed an increase of 6 cm in comparison to controls. The other studies are ongoing, but preliminary data is promising with improvements of standard deviation scores for height from baseline as well as improvements in predicted adult height based on bone ages. Finally, the available short-term data for safety are reassuring, however long-term data is lacking. **Findings from Past Animal Experiments**

NA

4. RADIOISOTOPES OR RADIATION MACHINES

a. Standard of Care (SOC) Procedures

Name of Exam Identify if SOC or Research

B	one age	Standard of Care
D	EXA	Standard of Care
La	ateral spine film	Research

b. Radioisotopes

i. Radionuclide(s) and chemical form(s)

NA

ii. Total number of times the radioisotope and activity will be administered (mCi) and the route of administration for a typical study participant

NA

iii. If not FDA approved: dosimetry information and source documents (package insert, Medical Internal Radiation Dose [MIRD] calculation, and peer reviewed literature)

NA

c. Radiation Machines – Diagnostic Procedures

i. Examination description (well-established procedures)

Annual bone age x-ray, and lateral spine film at baseline and 2 years Setup and techniques to support dose modeling

Standard radiography

iii. FDA status of the machine and information on dose modeling (if procedure is not well-established)

Well established clinical radiography

d. Radiation Machines – Therapeutic Procedures

i. Area treated, dose per fraction/number of fractions, performed as part of normal clinical management or due to research participation (well-established procedures)

NA

ii. FDA status of the machine, basis for dosimetry, area treated, dose per fraction and number of fractions (if procedure is not well-established)

NA

5. DRUGS, BIOLOGICS, REAGENTS, OR CHEMICALS USED IN THE STUDY

a. Investigational Drugs, Biologics, Reagents, or Chemicals

Investigational Product 1		
Name:	NA	
Dosage:	NA	
Administration Route:	NA	

b. Commercial Drugs, Biologics, Reagents, or Chemicals

Commercial Product 1		
Name:	Letrozole (no longer being used)	
Dosage:	2.5 mg	
Administration Route	Oral	
New and different use? (Y/N)	Yes	
Commercial Product 2		
Name:	Anastrozole	
Dosage:	1 mg	
Administration Route	Oral	
New and different use? (Y/N)	Yes	

6. **PARTICIPANT POPULATION**

a. Planned Enrollment

120; boys with short stature and/or growth hormone deficiency which may be congenital or acquired (post surgical or chemotherapy)

b. Age, Gender, and Ethnic Background

Males 10-17.99 years old, any ethnic background (identical to our clinical population) were recruited; those over 18 years old at f/u are reconsented,

c. Vulnerable Populations

The study is directed towards children because the purpose of the study is to evaluate growth. We will be monitoring for side effects closely.

d. Rationale for Exclusion of Certain Populations

All boys who fit under our inclusion criteria, regardless of ethnic background, will be included. Girls are excluded as aromatase inhibitor therapy will increase testosterone, causing untoward effects for girls.

e. Stanford Populations

None

f. Healthy Volunteers

None

g. Recruitment Details

The first person identifying patients for recruitment will be physicians in the Pediatric Endocrine Division at Lucile Packard. The protocol director will then continue the recruitment process in more detail.

h. Eligibility Criteria

i. Inclusion Criteria

Outpatient males with: Age 10-17.99 years; re-consented if over 18 years old at follow up Current height less than 5th percentile OR Predicted adult height (based on bone age) more than 10 cm below target height (mid parental height)

- Lab evidence of puberty: serum LH >0.3 IU/L and testosterone >15 ng/dl
- ii. Exclusion Criteria

Bone age xray more than 14 years FSH >20 IU/L

i. Screening Procedures

Pediatric endocrinologists will recruit all patients who qualify based on our inclusion criteria. Qualifying labs and bone age xray are usually obtained as part of routine clinical assessment of boys with short stature and/or delayed puberty, or would be obtained after enrollment and consent.

j. Participation in Multiple Protocols

We will ask the patients about other studies they may be enrolled in although we do not anticipate that this will occur.

k. Payments to Participants

No payments

I. Costs to Participants

Clinic visits, drugs, and laboratory charges which are considered standard of care will be the patient's responsibility.

m. Planned Duration of the Study

We anticipate the average length of treatment to be 2-3 years. We will evaluate the patients every 6 months with laboratory evaluation with the same frequency. After treatment, follow-up visits will be scheduled annually until growth is completed, which will be on average an additional 3-4 years (6-7 years from start of treatment). Subjects will be re-consented upon reaching 18 years of age.

7. RISKS

a. Potential Risks

i. Investigational devices

None

ii. Investigational drugs

None

iii. Commercially available drugs, biologics, reagents or chemicals

1) Arthralgia - reported in post-menopausal women at a frequency rate of 20-35%, lower in premenopausal women. Arthralgias have NOT been reported in the pediatric population.

2) Bone health - In adult women, there has been a reported decrease in bone mineral density by 6-7% after 5 years of therapy. We only have short-term data for young boys. Preliminary 1 year data did not show a difference in DEXA- measured bone mineral density in growth hormone (GH) deficient boys using Anastrozole in combination with GH. In boys with idiopathic short stature, there was no statistical difference between the treatment group using Letrozole versus the control group.

3) Fertility - In estrogen receptor knockout male mice, there is a progressive impairment of fertility. In one study using anastrozole in GH deficient boys, there was no difference in sperm parameters.

4) Metabolic parameters: lipids, insulin - In adult men with aromatase deficiency, increased cholesterol and increased insulin resistence has been descibed. In one study using Letrozole in pubertal boys, there was a significant decrease in HDL cholesterol, but all other lipids were unaffected. No changes have been reported in insulin sensitivity.5) Higher than normal testosterone levels could cause hair loss or behavioral changes. Neither has been reported in studies to date.

6) Growth velocity - excessive reduction in growth rate, which seems more likely to occur during the suppression of estrogen levels with Letrozole therapy. Procedures

Blood draws at each visit. Bone age annually. DEXA scan and lateral spine film at baseline and two years into the study. Radioisotopes/radiation-producing machines

DEXA scan which has less radiation than a standard chest XRAY; bone age and lateral spine x-ray. Physical well-being

Routine clinical history. Psychological well-being

Routine clinical history. Economic well-being

None

ix. Social well-being

None

x. Overall evaluation of risk

Medium International Research Risk Procedures

NA

c. Procedures to Minimize Risk

We will be monitoring for arthralgia with the clinical history every 6 months. We will also collect laboratory data every six months: lipids, insulin levels, as well as estrogen and testosterone, gonadotropin and growth hormone levels. We will perform DEXA scans at baseline and two years into study to assess for decreases in bone density. Access to the labs/scans are all password protected.

d. Study Conclusion

The endpoint is final height. We will terminate when the growth rate has decreased to less than 2 cm per year. Since we will be monitoring clinical and performing physical exams every 6 months, if any of the side effects have been clinically significant, we will treat accordingly and/or terminate the use of the therapy.

e. Data Safety Monitoring Plan (DSMC)

i. Data and/or events subject to review

We will be monitoring, through laboratory evaluation, lipids, insulin sensitivity, gonadotropins, sex steroids, and growth hormone levels. We will monitor for changes in bone density through DEXA scans. Person(s) responsible for Data and Safety Monitoring

Protocol Director Frequency of DSMB meetings

All labs/scans will be monitored as soon as theyhave been received from the reference lab. Specific triggers or stopping rules

Physician's clinical assessment based on laboratory evaluation. DSMB Reporting

As needed

vi. Will the Protocol Director be the only monitoring entity? (Y/N)

Yes

vii. Will a board, committee, or safety monitor be responsible for study monitoring? (Y/N)

No

f. Risks to Special Populations

Short-term studies of aromatase inhibitors in this age group have not shown any significant risks, but there is a theoretical risk of issues with bone density, testicular function, and alterations to lipids/carbohydrate metabolism that is present. We will be monitoring for these risks during the course of the study. The direct benefit is increased ultimate height. We will be discussing these theoretical risks with the family in depth and will be obtaining assent from the subjects themselves. **BENEFITS**

Greater final height for the individual participant and possibly improved treatment options for future patients.

9. **PRIVACY AND CONFIDENTIALITY**

All participant information and specimens are handled in compliance with the Health Insurance Portability and Accountability Act (HIPAA) and privacy policies of Stanford University, Stanford Health Care, and Stanford Children's Health.

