Randomization to Letrozole vs. Anastrozole in Short Pubertal Males

NCT02137538

June 24, 2021

[name], Principal Investigator [name], Principal Investigator Stanford University Stanford, California 94305

Statistical Methods

Baseline auxologic and hormonal measures were summarized by treatment arm. Laboratory measures over time were presented as means with standard deviation, with key measures (total testosterone, estradiol, IGF-1) additionally displayed as boxplots by arm. Growth velocity (cm/year), height (cm), bone age (months), predicted adult height (cm), and DEXA z-scores over time were similarly visualized. Adverse events were listed by arm, and spinal film was assessed qualitatively.

To include all patients in an intent-to-treat approach, mixed effects linear regression was used to model each outcome as a function of treatment arm, indicators for follow-up timepoints, and their interaction for assessing effect modification of annual change by arm. Within-patient correlation was accounted for by a random effect. Estimated change since baseline with 95% confidence intervals were presented by arm if effect modification was deemed significant at the 0.05 alpha level and as an overall effect otherwise. All analyses were performed in the R statistical computing framework, version 4.0¹.

¹ R Core Team (2020). R: A language and environment for statistical computing. R Foundation for Statistical Computing, Vienna, Austria. URL https://www.R-project.org/

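### Protocol 7f calls lipid changes a theoretical risk although 7a.iii reports an observed HDL fall in pubertal boys on letrozole, and the SAP does not commit to reporting HDL change by arm

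*Protocol*

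**What the plan says.** Protocol 7f (Risks to Special Populations) states that "Short-term studies of aromatase inhibitors in this age group have not shown any significant risks" and continues that "there is a theoretical risk of issues with bone density, testicular function, and alterations to lipids/carbohydrate metabolism that is present". It then says "We will be discussing these theoretical risks with the family in depth".

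Protocol 7a.iii item 4 (Metabolic parameters) reports: "In one study using Letrozole in pubertal boys, there was a significant decrease in HDL cholesterol, but all other lipids were unaffected". The item gives no size, SD, sample size or p-value for that decrease. It reports no lipid result for boys on anastrozole, and it says that no changes in insulin sensitivity have been reported.

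Protocol 7c provides the data: "We will also collect laboratory data every six months: lipids, insulin levels, as well as estrogen and testosterone". Lipids are also among the data under safety review in 7e. Section 1 makes comparison of the two drugs' side-effect profiles an aim of the study.

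The SAP presents laboratory measures over time as means with SD, "with key measures (total testosterone, estradiol, IGF-1) additionally displayed as boxplots by arm". It fits a mixed model to each outcome, with arm, timepoint and their interaction, but attaches no list of outcomes to that phrase. Change since baseline is given by arm if the interaction is significant at 0.05, and as one overall effect otherwise. Neither HDL nor lipids appear by name.

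**The concern.** Two things are at stake.

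The first is the accuracy of the risk description. Section 7f sets out what is to be discussed with families. Followed as written, it presents as theoretical a laboratory change that the same protocol, in 7a.iii, says was observed in pubertal boys on one of the two randomised drugs. The trial population is pubertal boys: the inclusion criteria in section 6h require laboratory evidence of puberty.

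The second is the safety comparison. Of the laboratory effects listed in 7a.iii, HDL is the only one with a reported significant change in boys. The SAP does not tell the reader whether HDL is one of the modelled outcomes. If it is, the by-arm estimate depends on an interaction test, so a trial meant to compare side effects could report one HDL change averaged over both drugs.

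**Working it through.** The documents give no HDL figure to reproduce. The first check is a comparison of passages, and the second follows the SAP's reporting rule through.

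**Step 1. 7f against 7a.iii, effect by effect.**

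| Effect listed in 7f | What 7a.iii reports in boys | Does *theoretical* fit? |
|---|---|---|
| Bone density | No DEXA difference at 1 year on anastrozole with growth hormone; no statistical difference on letrozole against control | Yes |
| Testicular function | No difference in sperm parameters in one anastrozole study | Yes |
| Lipids: HDL | Significant decrease in one letrozole study | No, for letrozole |
| Lipids: other | Unaffected in that letrozole study | Yes |
| Lipids on anastrozole | No result reported | Yes, in that nothing has been observed |
| Carbohydrate metabolism | No change in insulin sensitivity reported | Yes |

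Only HDL on letrozole is misdescribed.

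**Step 2. Does the wording still matter after letrozole was dropped?** Section 2a ends randomisation at the March 2016 renewal. Section 6m puts average follow-up at 6-7 years from the start of treatment and requires re-consent at 18. A boy reaches 18 within that time if he started at age 18 − 6 = 12 or older (18 − 7 = 11 at the longer figure), and the entry range is 10-17.99 years. Many boys treated with letrozole would therefore pass through a second consent discussion. A boy who started just before March 2016 would on average be followed until 2022-2023 (2016 + 6 to 2016 + 7).

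**Step 3. The SAP reporting rule.** Let the mean HDL change be −d on letrozole and 0 on anastrozole, and let w be the weight that letrozole carries in a pooled estimate.

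- Interaction p < 0.05: change is reported by arm, about −d and 0.
- Interaction p ≥ 0.05: one overall change is reported, about w × (−d) + (1 − w) × 0 = −w·d.

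With equal weights (w = 1/2), the single reported figure is half the letrozole fall. If boys enrolled to anastrozole alone after March 2016 are in the analysis, which the SAP does not say, w is smaller and the dilution greater. A p-value above 0.05 does not show that the drugs have the same effect; the difference with its confidence interval is the informative quantity, and the rule does not require it.

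**Step 4. Can precision be stated?** The 95% CI half-width for the difference in mean change is about t × SD × √(1/n_L + 1/n_A). The documents do not give the HDL SD, n_L or n_A. Planned enrolment of 120 (section 6a) does not supply n_L, because randomisation stopped and later boys received anastrozole only. No figure is offered.

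**The case against.** **The word *significant* may be used in two senses.** 7a.iii describes one study's result for one analyte, while 7f can be read as speaking of clinically important risks; 7d uses clinical significance for side effects. This stands against 7f's statement that no significant risks were shown: a reader might infer a flat contradiction there, and the text does not force one. It does not rescue *theoretical*, since a measured change is observed whatever its clinical weight.

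**The risk is named and monitored.** 7f lists lipids, 7c collects them every six months, and 7e puts them under review. This is correct, and it makes the point one of accurate labelling.

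**Families were misinformed.** A reader might infer this from 7f. The documents do not support it: the consent and assent pages are not available, and 7f only describes an intended discussion.

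**The SAP leaves HDL out.** A reader might infer this from the three key measures. That list only selects which laboratory measures get extra boxplots; it is not a hierarchy of outcomes. HDL falls under laboratory measures summarised as means with SD, and may well be among the modelled outcomes. What remains is that HDL is not named and that its by-arm reporting is conditional.

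**HDL is where the drugs are most likely to differ.** This is also tempting and also unsupported. With no anastrozole lipid result there is no basis for expecting a difference. The letrozole-specific signal in 7a.iii is item 6, on estrogen suppression and growth rate, and estradiol is already a key measure.

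**The correction comes late.** Letrozole is listed as no longer used, and the June 2021 SAP is written in the past tense. Few if any new families would hear a corrected letrozole statement. That limits the effect of the change but does not remove the case for re-consent of treated boys or for the side-effect comparison.

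**Conclusion.** The point holds in a narrow form. 7f groups an HDL decrease, observed on letrozole in one study of pubertal boys, with effects that are properly called theoretical, and it should be reconciled with 7a.iii item 4. The SAP's conditional by-arm rule fits poorly with the stated aim of comparing side effects, and HDL is the clearest laboratory instance of that.

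The size is modest. The wording error concerns one analyte on one drug and changes no endpoint. The SAP gap concerns how a result is reported; it does not show that HDL was left unanalysed. The conclusion rests only on the documents' text and needs no assumed HDL SD or arm size. It would be wrong to extend it to all lipids, because 7a.iii says the others were unaffected. Taking 120/2 = 60 per arm as the basis for a precision claim would also be wrong, because it presumes that all 120 were randomised.

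**What to change.** **Protocol 7f.** Reconcile it with 7a.iii item 4. 7f, and the discussion it describes (including re-consent at 18 of boys treated with letrozole), should say that an HDL decrease has been observed on letrozole in one study, that 7a reports no lipid result in boys on anastrozole, and that other lipid and carbohydrate effects remain theoretical.

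**SAP.** Name HDL cholesterol as a safety outcome. Report its change since baseline by arm, and the letrozole-minus-anastrozole difference with a 95% CI, whatever the interaction p-value. State the number of boys per arm contributing at each timepoint. Because the SAP is dated June 2021 and describes analyses already done, label this as an added analysis.

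**Cost.** A few sentences in 7f and one named outcome, using lipids already drawn every six months. The downsides are a less favourable risk statement and one more safety outcome without multiplicity control, so its interval should be read as descriptive.

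### Testicular function is said to be monitored, but its only named measures are hormones drawn largely on drugs that raise testosterone, and the SAP does not separate the off-medication values

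*Protocol*

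**What the plan says.** Comparing the side-effect profiles of the two drugs is a stated purpose (protocol section 1). Section 7a lists fertility among the risks, and section 7f describes a "theoretical risk of issues with bone density, testicular function, and alterations to lipids/carbohydrate metabolism that is present. We will be monitoring for these risks".

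The measures are listed in three places:
- Section 2a: "Labs (gonadotropins, androgens, estrogens, growth factors, lipid profile) will be done every 6 months".
- Section 7c: "lipids, insulin levels, as well as estrogen and testosterone, gonadotropin and growth hormone levels".
- Section 7e.i, data subject to safety review: "lipids, insulin sensitivity, gonadotropins, sex steroids, and growth hormone levels".

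None of these lists names a semen measure, testicular volume or any other direct test. Sperm parameters appear only in section 7a, as a result from an earlier study. Physical examinations are planned, but their content is not specified.

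On the drug effect, section 6d says that "aromatase inhibitor therapy will increase testosterone", and the Background section gives the mechanism: "Aromatase inhibitors block the conversion of testosterone to estrogen leading to more time for skeletal growth".

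Section 2a also says the staff will "repeat the above blood tests at least once off medication". It does not say how long after the last dose.

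The SAP states: "Laboratory measures over time were presented as means with standard deviation, with key measures (total testosterone, estradiol, IGF-1) additionally displayed as boxplots by arm". Gonadotropins are not among the key measures. Each outcome is modelled by arm, follow-up timepoint and their interaction. Change is shown by arm only if the interaction is significant at 0.05, and as one overall effect otherwise. No term or table separates values taken on drug from values taken after stopping.

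**The concern.** The other monitored risks in section 7f have a measure that addresses them directly: DEXA for bone, lipid and insulin assays for metabolism. Testicular function has only hormones, and for one of these, testosterone, the protocol itself says treatment pushes the value up. Both randomised arms received an aromatase inhibitor, so no untreated arm shows what puberty alone would have done. If one drug gives higher testosterone than the other, the reason may simply be stronger drug action.

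At stake is what the report can say about one named safety risk, and about a drug difference in it. The population includes boys with acquired growth hormone deficiency after surgery or chemotherapy. The plan already provides for samples that avoid the drug effect, but assigns them no separate role in the analysis.

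**Working it through.** The documents give no figure for this point, so there is none to reproduce. Two things can be checked: how many of the draws are on drug, and whether the SAP model can tell on-drug from off-drug values.

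**Step 1: inputs**
- Laboratory draws every 6 months on treatment, that is 2 per year (sections 2a and 6m).
- Average treatment length 2 to 3 years (6m).
- Annual follow-up after treatment, on average 3 to 4 more years (6m).
- Off-drug draws: at least 1 (2a). The procedures item in 7a says blood is drawn at each visit. If that covers follow-up, there would be 1 per year, so 3 to 4.
- The baseline draw is left out.

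**Step 2: on-drug share = on / (on + off), with on = 2 x years treated**

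| Years treated | On-drug draws | Off-drug draws | On-drug share |
|---|---|---|---|
| 2 | 4 | 1 (guaranteed minimum) | 4/5 = 80% |
| 3 | 6 | 1 (guaranteed minimum) | 6/7 = 86% |
| 2 | 4 | 3 (every annual visit) | 4/7 = 57% |
| 2 | 4 | 4 (every annual visit) | 4/8 = 50% |
| 3 | 6 | 3 (every annual visit) | 6/9 = 67% |
| 3 | 6 | 4 (every annual visit) | 6/10 = 60% |

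The range is 50% to 86%. On-drug draws are the majority in every case but one, which is an even split.

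**Step 3: what an on-drug testosterone contains.** It has at least three sources:
- the drug effect, stated in 6d;
- puberty, since boys may enter with testosterone just above 15 ng/dl and a bone age up to 14 years (6h);
- testicular output, which is the quantity of interest.

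The first two push the value up over 2 to 3 years. A normal or high value is therefore compatible with both preserved and reduced testicular function. With no untreated arm, the three cannot be separated from on-drug values.

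**Step 4: whether the SAP model separates them.** Its terms are arm, timepoint and arm by timepoint. Timepoint does not stand in for drug status, because treatment length varies. At 36 months, a boy treated for 2 years has been off drug for 12 months, while a boy treated for 3 years is just finishing. Both enter the same cell. Section 2a also allows reduction or discontinuation if growth velocity falls too far, and 7a regards such a fall as more likely on letrozole. The mix of on-drug and off-drug values at a timepoint may therefore differ by arm.

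**The case against.** Several counter-arguments have force.

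- **No document reads high testosterone as reassuring.** A reader might infer that rising testosterone would be reported as normal testicular function, or that the drug raising it more would look safer. The documents do not support this. Section 7a lists higher than normal testosterone as a risk in itself. What remains is that no document says how far an on-drug value bears on testicular function.
- **Gonadotropins are also measured.** A reader might infer that impairment would be hidden in these too. The documents do not state the drug effect on gonadotropins or its direction. A high on-drug FSH may still be a signal, and section 7e has laboratory results looked at on receipt. The argument is therefore confined to testosterone.
- **The off-drug repeat limits any masking of lasting impairment.** This stands. One well-timed off-drug panel may be informative however many on-drug samples precede it, and the on-drug share is only a rough measure. But the timing is not set, and the SAP does not single the sample out.
- **The SAP does not exclude off-drug values.** Correct. They fall under its laboratory summaries and model. They are undistinguished, not discarded.
- **Entry criteria screen for marked gonadal failure.** Boys with FSH above 20 IU/L are excluded, and minimum LH and testosterone values are required (6h). This lowers the concern at entry, including after chemotherapy. It does not address change during treatment.
- **The risk is called theoretical and the endpoint is final height.** True, and it limits the weight of the point. Physical examinations might also include a testicular examination, although none is named.

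**Conclusion.** The point holds in limited form. Testicular function is said to be monitored. The named measures that bear on it are testosterone (or androgens) and gonadotropins, with 50% to 86% of post-baseline draws on drug. Normal or raised on-drug testosterone, or an arm difference in it, is not evidence about testicular function. The SAP does not use the planned off-medication repeat to fill that gap.

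The share assumes the protocol's average treatment and follow-up lengths, no missed draws, and between one off-drug draw and one per follow-up year. The direction of the testosterone effect is the protocol's own statement.

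How large an impairment could go unseen cannot be computed, because the documents give no testosterone or gonadotropin values, no SDs and no size for the drug effect. This is a worthwhile low-cost improvement to the side-effect comparison. It does not touch the final-height endpoint.

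**What to change.** In the SAP:
1. Flag each hormone value as on or off drug at the time of the draw.
2. Report off-medication FSH, LH and testosterone separately by arm. Give the between-arm difference with 95% CI among randomised boys, and the time since last dose. Show this whether or not the interaction test reaches 0.05.
3. Keep boys treated after randomisation ended at the March 2016 renewal out of that between-arm contrast.
4. State that normal or raised on-drug testosterone will not be taken as evidence of preserved testicular function, and that fertility itself is not assessed.

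Section 7f of the protocol should carry the same limit in its wording.

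The cost is a few sentences and one small table from samples already planned. No test or visit is added. The downside is fewer samples per boy, hence a less precise comparison, and a narrower safety statement.
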